#### **7.5.3.3 Mean reduction from Baseline in estimated glomerular filtration rate (eGFR)**

Mean change and % mean change from baseline (defined as Visit 1a) in eGFR (mL/min/1.73m^2) will be summarized and analyzed similarly to that for the serum creatinine.

#### **7.5.3.4 Occurrence of MAKE**

Proportions of subjects with (1) either MAKE30, MAKE60, or MAKE90, (2) MAKE30, (3) MAKE60, and (4) MAKE90 will be calculated and analyzed using the Fisher's exact test as described for the reduction in urine output.

#### **7.5.3.5 Hospitalization parameters**

Number of days on ventilator, number of days in intensive care unit and length of hospital stay will be summarized by treatment group with descriptive statistics of mean, median, and SD. Appropriate statistical tests will be applied for the between treatment comparison. Exploratory analysis may be carried out using the Kaplan-Meier survival method. The between treatment difference will be tested using the log-rank test. Proportion of subjects who are re-admitted to the hospital after the initial hospital stay for the cardiac surgery will be calculated for Days 30, 60, and 90 and analyzed using the Fisher's exact test.

Additionally, the association between hospital parameters and the primary efficacy endpoint (as well as HO-1, IL-10, and ferritin) will be explored graphically by X-Y scatter plot and curve fitting for each treatment group.

As an exploratory analysis, numbers of days on ventilator, in ICU, and in the initial hospitalization, and hospital readmission rate will be summarized by the below subgroup.

- Type of surgery (CABG vs valve vs CABG and valve combined)
- Inpatient vs outpatient for the initial hospitalization
- CKD vs non-CKD
- Number of risk factors at baseline ( $\leq 2$  vs  $>2$ , and 0, 1-2,  $\geq 3$ )

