### 5.3.4 Hospitalization Parameters

Parameters related to hospitalization are as follows:

- Number of days on ventilator
- Number of days in intensive care unit (ICU)
- Hospital length of stay in days
- Readmission rate, defined as the proportion of subjects who are readmitted to a hospital following discharge from the initial hospitalization for CABG and/or cardiac valve surgery

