**LIST OF FIGURES**

Figure 14.2-2.1 Kaplan-Meier Plot for Duration of Hospital Stay for the Initial Hospitalization - MITT Population

Figure 14.2-2.2 Kaplan-Meier Plot for Duration of ICU for the Initial Hospitalization - MITT Population

Figure 14.2-2.3 Kaplan-Meier Plot for Days on Ventilator for the Initial Hospitalization - MITT Population

Figure 14.2-2.4 Kaplan-Meier Plot for Time to First Hospital Readmission - MITT Population

Figure 14.2-2.5 Kaplan-Meier Plot for Duration of First Hospital Readmission - MITT Population with Hospital Readmission

Figure 14.2-3.1 Scatter Plot with LOESS Curve Fitting for Days on Ventilator Over GM of Max PreOp/Baseline Preconditioning Biomarkers by Treatment Group

Figure 14.2-3.2 Scatter Plot with LOESS Curve Fitting for Days in ICU Over GM of Max PreOp/Baseline Preconditioning Biomarkers by Treatment Group

Figure 14.2-3.3 Scatter Plot with LOESS Curve Fitting for Days in Hospital Over GM of Max PreOp/Baseline Preconditioning Biomarkers by Treatment Group

Figure 14.2-4.1 Scatter Plot with LOESS Curve Fitting for Days on Ventilator Over Max PreOp/Baseline in Serum HO-1 by Treatment Group

Figure 14.2-4.2 Scatter Plot with LOESS Curve Fitting for Days in ICU Over Max PreOp/Baseline in Serum HO-1 by Treatment Group

Figure 14.2-4.3 Scatter Plot with LOESS Curve Fitting for Days in Hospital Over Max PreOp/Baseline in Serum HO-1 by Treatment Group

Figure 14.2-5.1 Scatter Plot with LOESS Curve Fitting for Days on Ventilator Over Max PreOp/Baseline in Serum IL-10 by Treatment Group

Figure 14.2-5.2 Scatter Plot with LOESS Curve Fitting for Days in ICU Over Max PreOp/Baseline in Serum IL-10 by Treatment Group

Figure 14.2-5.3 Scatter Plot with LOESS Curve Fitting for Days in Hospital Over Max PreOp/Baseline in IL-10 by Treatment Group

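### Ventilator, ICU and hospital days are analysed as plain durations with no rule for in-hospital death, so early deaths that differ between arms can make the arm with more deaths look no worse, or better

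*SAP*

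**What the plan says.** SAP 5.3.4 lists the endpoints as counts; the hospital one reads "Hospital length of stay in days". Death is not mentioned there.

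SAP 7.5.3.5 gives three layers of analysis:

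- Description: the day counts "will be summarized by treatment group with descriptive statistics of mean, median, and SD".
- Testing: "Appropriate statistical tests will be applied for the between treatment comparison". No test is named.
- Time to event: "Exploratory analysis may be carried out using the Kaplan-Meier survival method", followed by "The between treatment difference will be tested using the log-rank test". The event and the censoring rule are not defined.

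The SAP list of figures includes "Kaplan-Meier Plot for Duration of Hospital Stay for the Initial Hospitalization - MITT Population", with matching plots for ICU and ventilator time, and scatter plots of each duration against the preconditioning biomarkers.

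SAP 7.5 assigns these endpoints to the MITT population. SAP 3.2 requires MITT subjects to have been evaluated to the end of the index hospitalization, and does not say whether a subject who dies in hospital meets that condition.

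Elsewhere, death is a component of MAKE (SAP 5.3.3, defined for subjects with AKI) and appears in the safety outputs (SAP 6.3 and 7.6.1). The only general censoring statement, in Protocol section 12, concerns withdrawal.

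**The concern.** A hospital stay can end by discharge alive or by death. A day count cannot tell the two apart, so a subject who dies on Day 3 contributes about 3 hospital days, a better value than most survivors will have. In a log-rank test of duration without a rule for death, the programmer must choose to count the death as the end of stay, censor it, or drop the subject. None of these records death as a bad outcome.

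These durations fill Tables 14.2-8.1 to 14.2-8.8, three Kaplan-Meier figures and the scatter plots that relate the biomarkers to the hospital course. If early deaths fall unevenly, a stay shortened by death could be read as a benefit, and the same subjects would sit at the favourable end of the scatter plots.

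**Working it through.** **No figure to reproduce.** The documents give no power, event count or effect size for these three endpoints.

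**Inputs from the documents.** 42 subjects per arm (Protocol synopsis); two-sided 0.05 (SAP 7.2).

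**Assumed, because the documents do not give them.** Distribution of stay, and number and timing of in-hospital deaths. Ranges are shown below.

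**1. The mean, by arithmetic.** Let 42 subjects have 3 deaths, with every survivor staying 8 days.

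- Deaths on Day 2: (39 × 8 + 3 × 2) / 42 = 318 / 42 = 7.57 days.
- Deaths on Day 20: (39 × 8 + 3 × 20) / 42 = 372 / 42 = 8.86 days.

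Against 8 days with no deaths, early deaths shorten the mean and late deaths lengthen it. Timing decides the direction.

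**2. A rank comparison.** The SAP names no test, so Mann-Whitney stands in for it. Stay is log-normal with median 7 days and log-SD 0.45, with no true effect. There are 3 deaths against 0, falling on random subjects, and 4000 trials per setting. The table gives the share of trials in which the arm with the deaths has the lower mean rank, that is, looks better.

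| Day of death | Plain duration | Death ranked worst |
|---|---|---|
| 3 | about 70% | about 28% |
| 8 | about 48% | about 26% |
| 15 | about 30% | about 28% |
| 20 | about 29% | about 28% |

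Dropping the deaths at random gives 50%. With fewer Day-3 deaths the shares are 65% against 34% (2 vs 0) and 57% against 42% (1 vs 0). The worst-rank column is below 50% because the deaths count against that arm, as intended.

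**3. Log-rank, same set-up, 3 Day-3 deaths against 0.** Positive z means that the arm with the deaths looks better. Mean z is +0.37 with death as end of stay, 0.00 with death censored, and −1.14 with death as never discharged.

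**4. Log-rank when deaths fall mainly on the sicker subjects.** Stay is log-normal with median 7 and log-SD 0.5. Deaths are concentrated in subjects who would have stayed long. There are 1500 runs per setting. Cells give mean z and, in brackets, the share of runs falsely significant for a shorter stay in the arm with more deaths (nominal 2.5%).

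| Deaths, arm with more vs other | Timing | End of stay | Censored | Excluded | Worst outcome |
|---|---|---|---|---|---|
| 2% vs 2% | Days 1–4 | −0.01 (3.9%) | −0.01 (3.1%) | −0.01 (3.2%) | −0.01 (1.9%) |
| 7% vs 2% | Days 1–4 | +0.76 (15%) | +0.50 (9%) | +0.51 (9%) | −0.41 (0.4%) |
| 12% vs 2% | Days 1–4 | +1.26 (30%) | +0.75 (14%) | +0.78 (15%) | −0.87 (0.1%) |
| 20% vs 5% | Days 1–4 | +1.88 (47%) | +1.11 (24%) | +1.17 (26%) | −1.21 (0.0%) |
| 12% vs 2% | Days 10–24 | −0.34 (0.7%) | −0.65 (0.4%) | +0.84 (17%) | −0.85 (0.1%) |

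In the 12% vs 2% rows, mean stay in the arm with more deaths is 1.11 days shorter with early deaths and 0.30 days longer with late ones. Censoring and exclusion are neutral when deaths strike at random (steps 2 and 3). They favour the arm with more early deaths when the sickest die, because they remove long stays. Late deaths favour that arm only if they are excluded.

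**The case against.** The strongest reply is that the SAP is silent rather than wrong. A reader might infer that its methods count death as a short stay or censor it, and that an arm with more deaths will therefore look better. The documents do not support that inference. No section states that death is censored or defines the log-rank event, and the MITT wording permits a third reading in which in-hospital deaths are left out. The direction also depends on timing: with 3 deaths at Day 15 or Day 20, the plain comparison already runs against that arm about as strongly as worst ranking does. The documents give no death rate or timing.

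It is also fair to say that the SAP writes no rank test for these endpoints, that the means and medians are descriptive, that Kaplan-Meier is optional, and that the endpoints are exploratory. Deaths are visible by arm in the safety tables, and at this trial size a reader could notice 3 against 0.

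All of that stands as a limit on the claim. It does not remove the gap. A plain day count does record an early death as a short stay unless a rule says otherwise, and no rule does. The safety tables show that deaths occurred but do not correct the duration tables, the plots or the biomarker scatter plots.

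**Conclusion.** The point holds in conditional form. With early in-hospital deaths that are unequal between arms, the duration analyses can make the arm with more deaths look no worse, or better. For 3 Day-3 deaths against 0, the size is about 70% of null trials favouring that arm on ranks, against about 28% with death ranked worst. With 1 against 0 it is 57% against 42%. The difference is close to gone by Day 15 to 20, unless the deaths are excluded and fall on the sicker subjects.

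In the 3 against 0 case the shift in log-rank z is modest (+0.37 at most), so the risk is mainly one of direction. The larger false-positive rates, 14% to 30% at 12% vs 2%, need a larger early imbalance and deaths concentrated in subjects with long expected stays. All of these figures rest on assumed stay distributions, death rates and timings. It would go too far to say that the plan generally rewards mortality, or that it prescribes censoring at death. The primary conclusion is not affected.

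**What to change.** Before unblinding, add to SAP 5.3.4 and 7.5.3.5:

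1. In-hospital deaths stay in the analysis set for these three endpoints, with a matching clarification of the MITT definition in SAP 3.2.
2. Death is the worst outcome. Name a rank-based test with deaths placed beyond the longest observed stay; a version stratified by surgery type (van Elteren) would fit the rest of the SAP.
3. For Kaplan-Meier and log-rank, the event is discharge alive (or alive and off the ventilator, or alive and out of ICU). Deaths remain in the risk set to the end of follow-up and are not censored at death.
4. Show the number of deaths by arm beside each duration table and plot, and mark deaths in the scatter plots.

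Days alive and free of ventilator, ICU or hospital, or a competing-risk analysis of discharge alive, would be acceptable alternatives if specified in advance.

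The cost is a few lines of SAP text and a derivation rule, with no new data. The small downside is that ranks and medians replace means as the main summary.

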## **7.6 Safety Analysis**

The safety analyses described in this section will be conducted on the safety population.

### **7.6.1 Adverse Events**

AEs will be coded by system organ class (SOC) and preferred term according to the MedDRA dictionary (version 24.1).

TEAEs will be summarized for subject incidence rate. An overall summary of TEAEs that includes the total number of TEAEs reported, the number and proportion of subjects experiencing at least one TEAE, at least one severe TEAE, at least one treatment-related TEAE, at least one serious TEAE, at least one TEAE leading to study discontinuation, and at least one TEAE resulting in death will be displayed by treatment group.

The number and proportion of subjects experiencing a TEAE will also be presented by SOC and PT by treatment group.

Overall and by PT incidence rate will be summarized for subjects with TEAE of interest (Section 6.3) for each treatment group. Overall subject incidence rate for photosensitivity TEAEs will also be summarized for each treatment group.

A listing of all AEs will be provided. Separate listings will be created for all serious AEs, AEs leading to study discontinuation, and deaths.

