9.5.4 Dosage Preparation and Administration

Detailed instructions for dose preparation will be specified in the Pharmacy Manual.

Study drug (RBT-1 or placebo) will be administered via IV infusion over a 120-minute period ≥ 24 but ≤ 48 hours prior to scheduled cardiac surgery. Study drug administration may be performed in an outpatient setting.

Subjects will be observed for signs and symptoms of hypersensitivity during study drug administration and for at least 30 minutes after administration. Subjects should be

observed until they are deemed clinically stable. RBT-1 will only be administered when personnel and therapies are available for the treatment of any infusion-related reactions.

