### **6.1 Adverse Events**

Adverse Event means any untoward medical occurrence associated with the use of a drug in humans, whether or not considered drug related. An AE can be any unfavorable and unintended sign (e.g., an abnormal laboratory finding), symptom, or disease temporally associated with the use of a drug, without any judgment about causality.

All AEs will be recorded on the designated study eCRF for each subject beginning with the administration of investigational product and ending with the date of the end of study treatment follow-up (Day 90). AEs will be followed by the Investigator until event resolution, the subject is lost to follow-up, or the AE is otherwise explained or not considered clinically significant by the Investigator. AEs not resolved by Day 90 will be considered ongoing.

When reporting AEs, the Investigator will assess the relationship or association of study drug in causing or contributing to the adverse event as well as the intensity of the adverse event.

Treatment-emergent AEs (TEAEs) will be defined as any AE where the AE start date is on or after the infusion start date. AEs related to study treatment will be defined as any AE where the relationship to study treatment is considered as “possible” or “related”.

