### **6.4 Laboratory Parameters**

Screening laboratory samples will be processed at a local laboratory. All other laboratory samples will be processed at a central laboratory. For subjects who will be administered study drug on the same day of Screening, blood and urine samples will need to be collected for central laboratory analysis in accordance with Visit 1a.

Serum chemistry and hematology will be measured at Screening (Visit 0), Visit 1a, Day 1 PreOp (Visit 2), and on Days 2 to 7 (or discharge, whichever is earlier; Visits 3-8), Day 30 (Visit 9), Day 60 (Visit 10), and Day 90 (Visit 11). Serum CysC will only be measured at Visit 1a and on Days 30 (Visit 9) and 90 (Visit 11).

Serum chemistry parameters include total protein, albumin, bicarbonate, blood urea nitrogen (BUN), serum creatinine, total bilirubin, alkaline phosphatase, glucose, sodium, potassium, phosphate, calcium, magnesium, gamma-glutamyl transferase (GGT), alanine aminotransferase (ALT), aspartate aminotransferase (AST), and CysC.

Hematology parameters include RBC, hemoglobin, hematocrit, MCV, MCH, MCHC, platelets, MPV, RDW and WBC.

Blood and urinary biomarkers will be collected at Visit 1a, 1b, 2 (PreOp, 1h PostOp, 12h PostOp), 3 (Day 2) and 4 (Day 3).

Blood biomarkers include preconditioning response biomarkers (plasma HO-1, ferritin, and IL-10) and other biomarkers of RBT-1 activity and kidney function.

Urinary biomarkers include tubular injury biomarkers (KIM-1, CysC, and NGAL) and other biomarkers of RBT-1 activity and kidney function, which include but are not limited to urine albumin to creatinine ratio (UACR), urine protein to creatinine ratio (UPCR), beta-2-microglobulin, osteopontin, calbindin, clusterin, and VEGF.

Blood and urine samples may be collected by remote phlebotomy, such as through a mobile phlebotomist or other blood collection center, for a visit conducted virtually on Day 7, 30, 60, or 90.

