### **7.6.2 Laboratory Parameters**

Screening laboratory samples for chemistry, hematology and urinalysis will be processed at a local laboratory. All other laboratory samples will be processed at a central laboratory. For chemistry and hematology parameters, results at each visit will be summarized by treatment group. In addition, shift tables will also be presented within treatment groups.

All laboratory results will be listed.

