### **7.6.3 Other Safety Parameters**

Weight, body mass index, and vital signs (blood pressure, pulse rate, body temperature) at each scheduled visit and change from baseline at each visit will be summarized by treatment group. Physical examination results will be listed. Details of hospitalization(s) will be listed.

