**Clinial Laboratory Parameters**

Table 14.3-2.1 Summary of Hematology Test Results by Visit - Safety Population  
 Table 14.3-2.2 Summary of Chemistry Test Results by Visit - Safety Population  
 Table 14.3-2.3 Summary of Urinary Tubular Injury Biomarkers - MITT Population  
 Table 14.3-3.1.1 Subject Incidence of Hematology Test Result Shift from Baseline to the Highest Post Baseline - Safety Population  
 Table 14.3-3.1.2 Subject Incidence of Hematology Test Result Shift from Baseline to the Lowest Post Baseline - Safety Population  
 Table 14.3-3.2.1 Subject Incidence of Chemistry Test Result Shift from Baseline to the Highest Post Baseline - Safety Population  
 Table 14.3-3.2.2 Subject Incidence of Shift from Baseline to the Lowest Post Baseline Chemistry Parameters - Safety Population

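### No adverse-event table and no laboratory shift table is split at surgery, so early infusion effects on events common after cardiac surgery would be heavily diluted

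*SAP*

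**What the plan says.** Protocol 9.5.4 has study drug "administered via IV infusion over a 120-minute period ≥ 24 but ≤ 48 hours prior to scheduled cardiac surgery". SAP 6.1 sets the event window: "Treatment-emergent AEs (TEAEs) will be defined as any AE where the AE start date is on or after the infusion start date". Collection ends at Day 90, where Day 1 is the day of surgery (SAP 4.2).

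For the tables, SAP 7.6.1 states: "The number and proportion of subjects experiencing a TEAE will also be presented by SOC and PT by treatment group". Tables 14.3-1.1 to 14.3-1.9 in SAP 8 break these events down by preferred term, organ class, severity, relationship, seriousness and special interest. None is divided at surgery. The laboratory shift tables (14.3-3.1.1 to 14.3-3.2.2) use the highest or lowest post-baseline value, for example "Subject Incidence of Chemistry Test Result Shift from Baseline to the Highest Post Baseline - Safety Population".

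Other planned output does look at the time before surgery. SAP 7.6.2 says: "For chemistry and hematology parameters, results at each visit will be summarized by treatment group". SAP 6.4 places one of those visits after dosing and before the operation: "Serum chemistry and hematology will be measured at Screening (Visit 0), Visit 1a, Day 1 PreOp (Visit 2"). SAP 7.6.3 has vital signs "at each scheduled visit and change from baseline at each visit will be summarized by treatment group", and SAP 6.5 includes Day 1 PreOp among those visits. SAP 7.5.3.2 and 7.5.3.3 model creatinine and eGFR with active-versus-placebo differences at each visit, Day 1 included. Photosensitivity has its own summary by arm (SAP 7.6.1, Table 14.3-1.9).

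**The concern.** The interval between infusion and surgery is the only part of follow-up in which arms can be compared without the operation as a competing cause. The data to use it are already collected: Protocol 9.7.4.1 and 9.7.4.2 solicit adverse events separately before and after surgery on Day 1, and bloods are drawn pre-op.

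The events of interest in SAP 6.3 include atrial fibrillation, bleeding, delirium, vasoplegia and AKI, all plausible consequences of cardiac surgery. Protocol 6.1 puts postoperative AKI alone at about 30%. For such terms a table running from infusion to Day 90 cannot show whether an excess on active drug arose before the operation. In a shift table the Day 1 PreOp value counts only if no later value is more extreme.

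This matters because Protocol 11.4 justifies about 40 per group on safety grounds; its biomarker calculation asks for 6.

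**Working it through.** **The plan's own figure.** The documents give no event rate, detectable difference or power for safety, so there is nothing to reproduce. The figures below illustrate dilution and do not describe a planned test.

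**Share of the window.** Day 1 to Day 90 is 89 days. The pre-surgical interval is 1 to 2 days, so its share is 1/(1+89) = 1.1% to 2/(2+89) = 2.2%.

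**Inputs.** 42 per group (Protocol synopsis); two-sided 0.05 (SAP 7.2, used only as a yardstick). Assumed, because the documents give no rates: a pre-surgical event probability of 1% on placebo and 11% or 16% on one dose, and a surgical background b for the same term, equal in all arms and independent of the pre-surgical event.

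**Formula.** Pooled incidence = 1 − (1 − b)(1 − pre-surgical rate). The pooled risk difference is therefore (1 − b) times the pre-surgical difference. Example for 1% versus 16% at b = 0.30: placebo 1 − 0.70 × 0.99 = 30.7%; active 1 − 0.70 × 0.84 = 41.2%; difference 10.5 points, against 15 points before surgery.

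**Exact Fisher power by enumeration, 42 versus 42**

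| Surgical background b | Difference, 1% v 16% | Power, 1% v 16% | Power, 1% v 11% |
|---|---|---|---|
| none (pre-surgical table) | 15.0 points | 56% | 23% |
| 1% | 14.9 | 51% | 22% |
| 5% | 14.3 | 39% | 18% |
| 10% | 13.5 | 29% | 14% |
| 30% | 10.5 | 13% | 7% |
| 60% | 6.0 | 6% | 4% |
| 90% | 1.5 | 2% | 2% |

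**A second set of assumptions.** Let the drug add an independent 15% probability to a placebo pre-surgical rate of 2 to 5%. Power is 41 to 50% in the pre-surgical window, and pooled it is 12% at b = 30%, 6% at 60% and 2% at 90%. The pattern is the same.

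**What a pre-surgical table can rule out.** With 0 events in 42, the one-sided 95% upper bound is 1 − 0.05^(1/42) = 6.9%.

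**Which comparisons are already free of surgery**

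| Data | Planned comparison before surgery? |
|---|---|
| Chemistry and hematology, group summaries | Yes, Day 1 PreOp by arm (SAP 7.6.2) |
| Vital signs, with change from baseline | Yes, Day 1 PreOp by arm (SAP 7.6.3) |
| Creatinine and eGFR | Yes, modelled at Day 1, MITT (SAP 7.5.3.2, 7.5.3.3) |
| Laboratory shifts, subject level | No |
| Adverse events | No |

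On Day 1 the schedule has chemistry pre-op only, so the Day 1 creatinine contrast is a pre-surgical one. However, Table 14.2-5.2 is titled for post-operative visits and might omit it.

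**The case against.** The case against giving this much weight is substantial.

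- **Much of the comparison is already planned.** A reader might infer that the trial never makes a surgery-free safety comparison. The documents do not support that: the Day 1 PreOp summaries and the modelled creatinine and eGFR contrasts are such comparisons. This stands. What they leave out is adverse events, and the few outlying subjects whom a group summary can miss and a shift table is meant to catch.
- **Drug effects have other routes to view.** Photosensitivity, the main adverse event in Phase 1 (Protocol 6.4), has its own table. Events are also tabulated by relationship and listed in full, and SAP 4.3 counts event days from dosing. This stands in part. Relationship is an investigator's judgement that weighs the subject's clinical state (Protocol 10.2), and a listing is not a comparison between arms.
- **The dilution depends on the background.** A reader might infer that the planned tables have almost no ability to show an effect of the infusion. That fits only terms, or any-event totals, that are common after surgery. At a 1% background, power moves only from 56% to 51%.
- **No safety test is planned.** SAP 7.6 is descriptive, so power is only a gauge of lost signal. Even the split gives 23% for 1% versus 11%.
- **The gain is limited to early onset.** A drug effect appearing after surgery would still sit among surgical events. This stands.

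**Conclusion.** The point holds in a limited form. No treatment-emergent event table and no laboratory shift table is split at surgery, so the comparison of adverse events and of individual laboratory shifts free of surgery is missing from the plan. For terms or abnormalities common after cardiac surgery, an early infusion effect would be heavily diluted: the risk difference shrinks by the factor 1 − b, to 70% of its size at a 30% background and to 10% at a 90% background. For uncommon terms the loss is small.

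The size rests on assumed rates, on independence of pre- and post-surgical events, and on a background equal across arms. The structural finding needs none of these; it follows from the SAP's definitions and table list. It does not mean that laboratory and vital-sign safety before surgery goes unexamined, or that every drug effect would be hidden. The change is worth making because it is cheap and uses data already collected.

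**What to change.** Keep all overall tables and make these changes before unblinding.

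1. **SAP 7.6.1.** Add descriptive event tables by onset period: infusion start to start of surgery, and start of surgery to Day 90.
2. **Day 1 onsets.** Treatment-emergent events are defined by date only (SAP 6.1), so assign Day 1 events by onset time or by a before/after-surgery flag.
3. **Delayed or cancelled surgery.** State an analysis rule for treated subjects in this position. They remain in the Safety population (SAP 3.3), although MITT requires surgery without delay (SAP 3.2).
4. **SAP 7.6.2.** Add a Baseline-to-Day 1 PreOp shift table for chemistry and for hematology.
5. **Table 14.2-5.2.** Align the title with SAP 7.5.3.2 so that the Day 1 creatinine contrast is shown.

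The cost is SAP wording and a few more tables, with no new visit or sample. If onset times on Day 1 were not recorded, the flag would have to come from the separate pre-op and post-op solicitations. The split shows only effects that begin before surgery, and at about 42 per group it remains descriptive.
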